### **6.2.3 Recruitment**

#### **a. Subject selection must be equitable; i.e., male/female, age range, racial and ethnic origin:**

Subjects will be selected and randomized into each group without discrimination by gender, race, or ethnicity. A predominantly female population is expected based on the historical patient population for bariatric surgery.

**b. Describe method of screening subjects and indicate when, where and how study subjects will be recruited, if applicable:**

For a bariatric patient to make it to their appointment to schedule their surgery, they will have already been screened as part of standard of care. This screening includes: ensuring BMI and comorbidities meet requirements to qualify for surgery, laboratory tests looking for an organic cause of obesity, psychiatric evaluation, upper endoscopy with gastric biopsies, ultrasound of the gallbladder if present, and several counseling sessions. Once all requirements have been met, they are seen in the bariatric clinic. Patients may choose which bariatric procedure they desire based on the information provided at the educational conferences without any coercion by staff to pick one procedure over another for research purposes. The educational conference is standardized and will not change as a result of implementation of this study. Staff may recommend the gastric bypass to certain patients based on excessive BMI or comorbidities, but the patient ultimately decides which surgery they desire based on all the information they are provided. When a patient had elected for a sleeve gastrectomy, he/she will be invited to speak with a research resident listed on the protocol, and a flyer pertaining to the project will be available for the patient to arrange a meeting to discuss the project. The research project representative will meet the patient, and details of the study will be discussed in person with patient. Pertinent topics of discussion will be that two different companies manufacture FDA-approved devices that are used for sleeve gastrectomies. Neither has been proven superior, and the aim of this study is to see if our institution has better results with one particular device in an effort to improve future patient care. The patient will be seen the day of surgery by a research representative, and he/she will be able to opt in or out at that time if they desire.

**c. Compensation for participation:**

None

#### **6.2.4 Consent Process**

**a. Discuss how and when subjects will be consented, who will administer consent/HIPAA authorization and steps taken to prevent coercion.**

Patients will be consented in person and sign a written consent during their bariatric pre-operative visit or at a later time if the patient so chooses. The consent process will be performed by a research physician. Patients may opt out of the study at any time. All patients will be consented individually in a private space at their convenience. Any questions related to the study will be answered prior to signing the consent form.

**b. Discuss efforts made to promote subjects' understanding of the consent form:**

Patients will have already gone through extensive counseling on the surgeries as part of the department protocol. As this study looks at a part of the surgery that would occur without the study, they will already be familiar with the surgery. However, the details will be discussed again with the patient. A written consent will also be available. Someone is available to answer questions at any time. The patient will be seen the day of surgery by a research representative, and he/she will be able to opt in or out at that time if they desire.

**c. Justify Waiver of Consent/Waiver of HIPAA Authorization, Waiver of Documentation of Consent (consent without signature), if applicable:**

N/A

**6.3 Study Design and Methodology - As appropriate, the study design and methodology should include the following sub-sections.**

**6.3.1 Study Design Statement – *Describe in detail the type of study design including description of randomization/blinding and how any confounding variables will be controlled by study design:***

**a. Describe what will happen on this study that is RESEARCH/EXPERIMENTAL:**

Subjects will be randomly assigned to one of two devices as they are scheduled for surgery using a shuffled stack of cards. Despite being the same operation that would be performed without the study, data will be collected throughout the case and recorded for research purposes as mentioned above.

**b. Describe what will happen on this study that is STANDARD of CARE:**

All elements of this study abide by the standard of care. Up to this point, there's been no proof that one stapler brand is superior to the other, so using either stapler is current standard of care. Both devices are currently used at WBAMC. Currently, the Ethicon Echelon is more frequently used due to availability, but all bariatric surgeons are trained and comfortable with the Covidien iDrive. Subjects will have the same pre-operative work-up as described previously, they will undergo the same operation, and have the same post-operative care, medications, and follow-up as each other and their counterparts not enrolled in the study.

**6.3.2 Study Methodology/Procedures:**

Patients who express an interest in bariatric surgery will attend a bariatric seminar and initiate the process of scheduling bariatric surgery per department protocol. Once qualified for surgery, the patients will present to bariatric clinic, which takes place in the general surgery clinic on Tuesdays, and have a one-on-one discussion about their desired surgery with a staff physician. If the patient desires a sleeve gastrectomy, the study will be discussed. Consent will be obtained, and the patient will be randomized into the Covidien or Ethicon group. The subject will proceed with surgery per department protocol. In the operating room, a data collection sheet will be available in the operating room to make note of time for creation of sleeve from first firing to completion, total number of staple loads fired, number of misfires, character of any bleeding at the staple line and which interventions were required to control it, and time it takes for the surgical technologist to reload the stapler. At William Beaumont surgical technologists are trained on loading each linear cutting stapler by the Covidien and Ethicon representatives. We will still ensure at the start of the case they are familiar with loading the provided device. No additional training for device will be mandated, as surgical technologist turnover would make this difficult to provide equal training, and it would detract from internal and external validity, since we do not normally provide extra training. Typically the sleeve is created by staff or higher level residents (PGY-2 and above). However, all residents are trained on the devices and are therefore capable of creating the sleeve with close staff supervision, as is standard for our institution. For the purpose of this study, we intend on maintaining this practice since all level residents may be assisting and performing this surgery throughout their residency and deviation would lead to questionable internal validity. After surgery, patients will be admitted to the hospital, and care will follow the department's bariatric protocol. Once discharged, they will follow-up at 3 weeks, 6 weeks, 3 months, 6

months, and then annually. Subjects will be followed for 1 year after surgery. During that time, weight loss, presence of staple line leaks, any readmissions, and any other interventions will be monitored.

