**3. OBJECTIVES AND SPECIFIC AIMS:**

Primary objectives: Determine if using different brand staplers affects:

1. Time of creation of sleeve from first firing to completion
2. The percent of firings with technical difficulties
3. The time for tech to load each staple cartridge (aware of Hawthorne effect. Since both arms will be subject to Hawthorne effect, the only variable should be the stapler)

Secondary objectives: Determine if using different brand staplers affects:

1. Any bleeding after creation of the sleeve (annotating whether single or multiple interventions are required)
2. Weight loss
3. Leak rates
4. Hospital readmissions or emergency room visits (For complications including but not limited to dehydration, hemorrhage, leak, internal hernia, and pain; will annotate what complication warranted readmission)
5. Further sleeve interventions

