### **6.3.4 Data Collection (*all study variables/instruments/questionnaires to be administered*):**

There will be two separate data logs maintained for the purposes of this study. The first log (master key) will contain all subject identifiers and PHI. Specifically, the master key will include:

- Patient identifier (to be linked to study log)
- Patient name
- Date of birth
- Surgeon
- Date of operation
- Family member prefix with last four digits of the social security number

The second log (data collection sheet) will include patient identifier to link to master key, but include no other PHI or direct identifiers. A data collection sheet that omits identifiable patient health information (only a pre-assigned identifier unique to the study) will be present in the operating room. This information will be transcribed to a data log on a secure computer. Specifically, the data collection sheet will include;

- Patient identifier (to link to master key)
- Gender
- Race
- Age
- Pre-operative height (needed to calculate ideal body weight)
- Pre-operative weight
- Intra-operative data points, to include time to load stapler, time to create sleeve, intra-operative bleeding or leak, and number of staple load misfires
- Weight recordings from follow-up appointments
- Annotations of any re-admissions or complications after surgery
- Follow-up weight (at follow up points)
- Weight loss (at follow up points)
- Need for hospital readmission or emergency room visits with annotation of the complication that caused the increased need for hospital care

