#### **6.4.2 Data analysis:**

For the continuous primary endpoints, the two-sample t-test for 2 means will be used to compare the 2 Devices at Surgery. For the continuous secondary endpoints, such as weight loss, the General Linear Mixed Model Analysis for repeated measures over time will be used to test for the Device effect, Time effect and the Device by Time Interaction. For the binary secondary endpoints (Yes/No), such as Staple line leak, Readmission or ER visits, further sleeve interventions, over time, the General Estimating Equations (GEE) analyses will be used to test for Device effect, Time effect and the Device by Time Interaction. For all tests, the level of significance is set at 0.05.

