#### **6.4.3 Sample Size Estimation:**

75 in each arm for a total of 150 patients. The preliminary power analysis indicated 64 in each arm to be sufficient, to be able to detect a medium effect size of 0.5 for the two-sided t-test, with  $\alpha = 0.05$  and 80% power, so 11 extra patients per arm have been added for attrition. The power analysis was based on the research hypothesis of a difference in the 2 devices, with this superiority study using time to create sleeve as the primary variable.

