### 6.5.2 Expected Adverse Events from Research Risks and Reporting:

Overall, the risk of complications from sleeve gastrectomy generally falls in the less likely range (1%-5%). According to other studies that have been performed using both staplers, they did not report significant differences in staple line leaks. Additional risks as a result of this study are expected to fall in the rare but serious range (<1%). Such risks may include minor staple line bleeding which will be addressed in the operating room, which may be attributed to a surgeon using one stapling device less than another despite being fully trained for both. Post-operative staple-line leak, pain, dehydration, infection, and blood clots are also known complications of the surgery, but the study is not expected to alter the likelihood of these events.

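### Who fires and who loads the stapler is neither protected from knowledge of the allocated device nor recorded, so device-related staffing could bias the two timing endpoints unseen

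*Combined protocol and SAP*

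**What the plan says.** **Allocation.** Section 2.4 sets up one card folder per attending surgeon, each with 25 cards per device, and has the card drawn after consent. Section 6.3.1(a) places the draw at scheduling, and 6.3.2 places it in the clinic pathway before surgery. Section 2.3 calls the study single-blinded without naming the blinded party; the operating team necessarily sees the stapler.

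**Who fires.** Section 6.3.2: "Typically the sleeve is created by staff or higher level residents (PGY-2 and above". It adds that all residents are trained and may create the sleeve under close staff supervision, and that this practice will be kept.

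**Who loads.** The same section says technologists are trained on both devices by the manufacturers' representatives and are checked at the start of each case for familiarity with the device in use. It mandates no further training, citing turnover.

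**What is recorded.** Section 6.3.4 puts the attending surgeon in the master key. The data collection sheet lists "Intra-operative data points, to include time to load stapler, time to create sleeve, intra-operative bleeding or leak, and number of staple load misfires". Operator grade and technologist appear neither there nor in 6.3.2 or 6.3.5.

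**Familiarity.** Section 6.3.1(b): "Currently, the Ethicon Echelon is more frequently used due to availability", followed by the statement that all the bariatric surgeons are trained on and comfortable with the other device. Section 6.5.2 allows for minor staple-line bleeding "which may be attributed to a surgeon using one stapling device less than another despite being fully trained for both". For loading time, Sections 3 and 6.4.1 argue: "Since both arms will be subject to Hawthorne effect, the only variable should be the stapler".

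**Analysis.** Section 6.4.2 compares continuous primary endpoints with an unadjusted two-sample t-test.

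**The concern.** Sleeve time and cartridge loading time measure people using a device, so they depend on who is using it. Randomising cases protects the comparison only as long as staffing does not react to the allocation. Here the allocation can be known before the case is staffed, and there is no rule for assigning the operator or the technologist. A senior surgeon might take the stapler more readily when the less-used device has been drawn, or a technologist might be swapped after the device-specific check at the start of the case. Either would shift the times in one arm.

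Stratifying by attending surgeon balances the attendings. It does not balance who fires or who loads if those choices respond to the device. Because neither person is a listed data item, the planned dataset could neither reveal such a shift nor support an adjustment for it. Section 2 says the findings will guide which stapler the hospital prefers, so a staffing difference read as a device difference would have practical consequences.

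**Working it through.** **1. The plan's own figure.** Inputs from 6.4.2 and 6.4.3: "For all tests, the level of significance is set at 0.05"; "medium effect size of 0.5 for the two-sided t-test"; 80% power; sleeve time as the powered variable. The normal approximation gives n = 2(1.960 + 0.842)²/0.5² = 62.8, so 63 per arm. The noncentral t calculation gives 63.77, so 64, with 80.1% power. This agrees with "The preliminary power analysis indicated 64 in each arm to be sufficient". Adding 11 gives 75 per arm, where power is 86.0%. The sample size is not in dispute.

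**2. What stratification covers.** Three folders × 25 cards per device = 75 per arm, so attending surgeon is balanced by design once the folders are used up. Operator grade within surgeon, and technologist, are balanced only in expectation, and only if assigned without regard to device.

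**3. Assumptions.** The documents give neither an operator effect nor an imbalance. I assume:
- a difference in sleeve time between operator grades of g = 0.5 to 1.0 SD;
- a difference between arms in operator mix of m = 0 to 20 percentage points;
- for the noise calculation only, a resident-created share of p = 0.3 to 0.5.

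**4. If staffing is independent of device (m = 0).** Expected bias is g × 0 = 0. What remains is noise. With the SD within an operator grade set to 1, the share of variance due to grade is p(1−p)g²/[1 + p(1−p)g²]:
- g = 0.5: 0.0525/1.0525 = 5.0% (p = 0.3) to 0.0625/1.0625 = 5.9% (p = 0.5);
- g = 1.0: 0.21/1.21 = 17.4% to 0.25/1.25 = 20.0%.

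**5. If staffing responds to device.** Bias = g × m, in units of the SD behind the plan's 0.5. The table gives rejection probabilities for the planned t-test at 75 per arm (148 degrees of freedom, noncentrality = difference × √(75/2)).

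| g (SD) | m (points) | Bias (SD) | False-positive rate, no true difference | Power, bias opposing a true 0.5 SD |
|---|---|---|---|---|
| any | 0 | 0 | 5% | 86.0% |
| 0.5 | 10 | 0.05 | 6.1% | 78.2% |
| 0.5 | 20 | 0.10 | 9.3% | 68.2% |
| 1.0 | 10 | 0.10 | 9.3% | 68.2% |
| 1.0 | 20 | 0.20 | 22.9% | 44.6% |

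The largest bias is 0.20/0.5 = 40% of the target difference. If g is instead measured in within-grade SDs, as in step 4, then at g = 1.0 and p = 0.5 the total SD is √1.25 = 1.118. The largest bias is then 0.20/1.118 = 0.18, or 36% of the target.

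**6. The Hawthorne argument.** An observation effect common to both arms cancels from the difference in mean loading time. A different mix of technologists, or less practice with one device, is not common to both arms and does not cancel. The premise about observation therefore does not yield the conclusion that only the stapler differs in loading time.

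**The case against.** The best defence is that the documents show no biased staffing. That is correct, and several stronger readings that a reader might infer should be set aside.

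- *That the operator is chosen after the device is known.* The protocol says when the card is drawn; it does not say when or how operator or technologist is assigned. Only the lack of protection is established.
- *That randomisation fails to balance operators.* It balances them in expectation unless assignment responds to device, and the attending surgeon is both stratified and recorded.
- *That the protocol claims only the stapler varies for every primary endpoint.* That sentence is attached to loading time and answers the Hawthorne effect. The broader statement, in 6.5.1(c), is that technique should not differ apart from the stapler and its reinforcement.
- *That unequal familiarity confounds the comparison.* It does not. It defines the contrast as the device plus current local experience, which limits interpretation. Frequency of use is also only indirect evidence of familiarity: surgeons and technologists are trained on both devices, and 6.5.2 concerns possible minor bleeding, not times.

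Keeping usual staffing is also a reasoned pragmatic choice in 6.3.2. The list in 6.3.4 is not exhaustive either: it omits total loads fired, which 6.3.2 and 6.3.5 do record. But no section lists operator grade or technologist, so the gap in the data stands. So does the absence of any safeguard on staffing, and neither conflicts with the pragmatic aim.

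**Conclusion.** The point holds as a gap in safeguards and records, not as a demonstrated bias. The choice of who fires and who loads is not fixed before, or shielded from, knowledge of the device; the planned data would not show whether it differed by arm; and the primary t-test leaves out the factor used to stratify allocation. The last of these costs precision and does not bias the comparison.

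The bias in sleeve time ranges from none to 0.20 SD. That range rests entirely on the assumed operator effect and imbalance, and zero is as consistent with the documents as any other value in it. No separate figure is offered for loading time; the same mechanism applies through the technologist, and the Hawthorne argument does not remove it. The change is worth making because it is cheap and turns an unverifiable assumption into a checkable one.

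**What to change.** 1. Add to the data collection sheet the operator's grade (staff or PGY year), any change of operator during the case, and a technologist code.
2. Replace the t-test for sleeve time with a linear model for device adjusted for surgeon.
3. Report operator grade and technologist mix by arm. Where the planned operator can be named before the card is opened, for example by opening it on the day of surgery, adjust for planned grade. Otherwise use actual grade only in a sensitivity analysis, because it is a post-randomisation variable. Adjusting for planned grade does not remove bias from a later takeover, which is why changes during the case must be recorded.
4. State the contrast as the device as used at current local familiarity. Keep any device-by-case-order analysis within surgeon exploratory: there are only 25 cases per device per surgeon, and an attending's case order does not measure the experience of residents or technologists.

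The cost is two extra fields (operator grade with any change, and technologist code) on a sheet that a research resident already completes in the operating room, one model term, and possibly a later card opening. That last item may be awkward, since the draw now takes place in clinic, when the resident and technologist may not yet be known; items 1, 2 and 4 do not depend on it. Sample size, training and usual staffing are unchanged.

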### **6.3.3 Prospective Collection of Human Biological Specimens:**

No additional biological specimens will be obtained or banked exclusively for the purposes of this study.

### **6.3.4 Data Collection (*all study variables/instruments/questionnaires to be administered*):**

There will be two separate data logs maintained for the purposes of this study. The first log (master key) will contain all subject identifiers and PHI. Specifically, the master key will include:

- Patient identifier (to be linked to study log)
- Patient name
- Date of birth
- Surgeon
- Date of operation
- Family member prefix with last four digits of the social security number

The second log (data collection sheet) will include patient identifier to link to master key, but include no other PHI or direct identifiers. A data collection sheet that omits identifiable patient health information (only a pre-assigned identifier unique to the study) will be present in the operating room. This information will be transcribed to a data log on a secure computer. Specifically, the data collection sheet will include;

- Patient identifier (to link to master key)
- Gender
- Race
- Age
- Pre-operative height (needed to calculate ideal body weight)
- Pre-operative weight
- Intra-operative data points, to include time to load stapler, time to create sleeve, intra-operative bleeding or leak, and number of staple load misfires
- Weight recordings from follow-up appointments
- Annotations of any re-admissions or complications after surgery
- Follow-up weight (at follow up points)
- Weight loss (at follow up points)
- Need for hospital readmission or emergency room visits with annotation of the complication that caused the increased need for hospital care

A research resident listed on the protocol will be present during the operation to populate the data points on the data collection sheet. Timing, done by a physician, will require a stopwatch to monitor the total sleeve creation time and the time it takes to load each stapler cartridge. This data will be transcribed into the Excel data collection spreadsheet on a secure, password-protected computer. Data from follow-up visits, such as complications and weight, will be acquired via chart review through AHLTA and CHCS. The master key with patient identifiers will be linked to the data log sheet to allow physician researchers to acquire this information from the electronic medical records. All information will remain on a secure hospital computer and will be intermittently updated by a research resident as the study progresses. As listed above, information acquired from chart review during this study will include: follow-up weight, weight loss, and need for hospital readmission or emergency room visits with annotation of the complication that caused the increased need for hospital care. Other information, such as name, height, race, age, family member prefix with last four digits of the social security number, initial weight, surgeon, date of the operation, data points collected in the operating room (time to load stapler, time to create sleeve, intra-operative bleeding or leak, and number of staple load misfires) will

have already been added to the list shortly after the patient's procedure.

